## **6.3 TOXICITY CRITERIA**

The following adverse event management guidelines are intended to ensure the safety of each patient while on the study. The descriptions and grading scales found in the revised NCI Common Terminology Criteria for Adverse Events (CTCAE) version 4.0 will be utilized for AE reporting. All appropriate treatment areas should have access to a copy of the CTCAE version 4.0. A copy of the CTCAE version 4.0 can be downloaded from the CTEP web site ([http://ctep.cancer.gov/protocolDevelopment/electronic\\_applications/ctc.htm#ctc\\_40](http://ctep.cancer.gov/protocolDevelopment/electronic_applications/ctc.htm#ctc_40)).

# **7 NIH REPORTING REQUIREMENTS / DATA AND SAFETY MONITORING PLAN**

## **7.1 DEFINITIONS**

Please refer to definitions provided in Policy 801: Reporting Research Events found [here](#).

## **7.2 OHSRP OFFICE OF COMPLIANCE AND TRAINING / IRB REPORTING**

### **7.2.1 Expedited Reporting**

Please refer to the reporting requirements in Policy 801: Reporting Research Events and Policy 802 Non-Compliance Human Subjects Research found [here](#). Only IND Safety Reports that meet the definition of an unanticipated problem will need to be reported per these policies.

### **7.2.2 IRB Requirements for PI Reporting at Continuing Review**

Please refer to the reporting requirements in Policy 801: Reporting Research Events found [here](#).

## **7.3 NCI CLINICAL DIRECTOR REPORTING**

Problems expeditiously reported to the OHSRP in iRIS will also be reported to the NCI Clinical Director. A separate submission is not necessary as reports in iRIS will be available to the Clinical Director.

In addition to those reports, all deaths that occur within 30 days after receiving a research intervention should be reported via email to the Clinical Director unless they are due to progressive disease.

To report these deaths, please send an email describing the circumstances of the death to [name] at [[contact]](mailto:[contact]) within one business day of learning of the death.

## **7.4 NIH REQUIRED DATA AND SAFETY MONITORING PLAN**

### **7.4.1 Principal Investigator/Research Team**

The clinical research team will meet on a weekly basis when patients are being actively treated on the trial to discuss each patient. Decisions about enrollment will be made based on the toxicity data from prior patients.

All data will be collected in a timely manner and reviewed by the Principal Investigator or a Lead Associate Investigator. Events meeting requirements for expedited reporting as described in section [7.2.1](#) will be submitted within the appropriate timelines.

The Principal Investigator will monitor in real time the safety assessment of the first 6 lead in accrual subjects 101-106 for acute or subacute adverse events (other than local injection site reactions) determined to be possibly, probably or definitely related to vaccination occurring within 3 weeks of receipt of the first ME TARP DC vaccine dose. Initial staggered enrollment of the first 3 study subjects and subsequent enrollment will proceed as previously described.

The Principal Investigator and Lead Associate Investigator will be responsible for overseeing the Data and Safety Monitoring Plan with the assistance of personnel employed by a CCR contractor. As information is gathered from this trial, clinical results will be shared with the patients. Laboratory and clinical data will be gathered on a bi-weekly basis and any new significant observation(s) found during the course of the research that may affect patient safety or a patient's willingness to participate further will be explained at the time patients are consented for the study.

The Principal Investigator will review adverse event and response data on each patient to ensure safety and data accuracy. The Principal Investigator will personally conduct or supervise the investigation and provide appropriate delegation of responsibilities to other members of the research staff.

## **8 SPONSOR SAFETY REPORTING**

### **8.1 DEFINITIONS**

#### **8.1.1 Adverse Event**

Any untoward medical occurrence in a patient or clinical investigation subject administered a pharmaceutical product and which does not necessarily have a causal relationship with this treatment. An adverse event (AE) can therefore be any unfavorable and unintended sign (including an abnormal laboratory finding), symptom, or disease temporally associated with the use of a medicinal (investigational) product, whether or not related to the medicinal (investigational) product (ICH E6 (R2))

#### **8.1.2 Serious Adverse Event (SAE)**

An adverse event or suspected adverse reaction is considered serious if in the view of the investigator or the sponsor, it results in any of the following:

- Death,
- A life-threatening adverse event (see section [8.1.3](#))
- Inpatient hospitalization or prolongation of existing hospitalization

- A hospitalization/admission that is pre-planned (i.e., elective or scheduled surgery arranged prior to the start of the study), a planned hospitalization for pre-existing condition, or a procedure required by the protocol, without a serious deterioration in health, is not considered a serious adverse event.
- A hospitalization/admission that is solely driven by non-medical reasons (e.g., hospitalization for patient convenience) is not considered a serious adverse event.
- Emergency room visits or stays in observation units that do not result in admission to the hospital would not be considered a serious adverse event. The reason for seeking medical care should be evaluated for meeting one of the other serious criteria.
- Persistent or significant incapacity or substantial disruption of the ability to conduct normal life functions
- A congenital anomaly/birth defect
- Important medical events that may not result in death, be life-threatening, or require hospitalization may be considered a serious adverse drug experience when, based upon appropriate medical judgment, they may jeopardize the patient or subject and may require medical or surgical intervention to prevent one of the outcomes listed in this definition.

#### 8.1.3 Life-threatening

An adverse event or suspected adverse reaction is considered "life-threatening" if, in the view of either the investigator or sponsor, its occurrence places the patient or subject at immediate risk of death. It does not include an adverse event or suspected adverse reaction that, had it occurred in a more severe form, might have caused death. (21CFR312.32)

#### 8.1.4 Severity

The severity of each Adverse Event will be assessed utilizing the CTCAE version 4.0.

#### 8.1.5 Relationship to Study Product

All AEs will have their relationship to study product assessed using the terms: related or not related.

- Related – There is a reasonable possibility that the study product caused the adverse event. Reasonable possibility means that there is evidence to suggest a causal relationship between the study product and the adverse event.
- Not Related – There is not a reasonable possibility that the administration of the study product caused the event.

### 8.2 ASSESSMENT OF SAFETY EVENTS

AE information collected will include event description, date of onset, assessment of severity and relationship to study product and alternate etiology (if not related to study product), date of resolution of the event, seriousness and outcome. The assessment of severity and relationship to the study product will be done only by those with the training and authority to make a diagnosis and listed on the Form FDA 1572 as the site principal investigator or sub-investigator. AEs

occurring during the collection and reporting period will be documented appropriately regardless of relationship. AEs will be followed through resolution.

SAEs will be:

- Assessed for severity and relationship to study product and alternate etiology (if not related to study product) by a licensed study physician listed on the Form FDA 1572 as the site principal investigator or sub-investigator.
- Recorded on the appropriate SAE report form, the medical record and captured in the clinical database.
- Followed through resolution by a licensed study physician listed on the Form FDA 1572 as the site principal investigator or sub-investigator.

For timeframe of recording adverse events, please refer to section [6.1](#). All serious adverse events recorded from the time of first investigational product administration must be reported to the sponsor.

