### **Study Design:**

- Phase II, prospective, single-blinded, randomized, placebo controlled study in men with Stage D0 prostate cancer. Men with a PSADT  $\geq$  3 months and  $\leq$  15 months will be randomized 2:1 to receive ME TARP autologous DC vaccination or a control elutriated monocyte vaccine placebo.
- An initial lead-in of 6 patients will be enrolled to allow preliminary assessment of the safety of the ME TARP vaccine platform through 12 weeks before enrollment of prospectively randomized subjects blinded to treatment assignment begins.
- All patients will receive a total of 6 doses of vaccine ( $20 \times 10^6$  *viable* cells/dose) delivered intradermally at Weeks 3, 6, 9, 12, 15, and 24. All patients will undergo a 15-18L apheresis at Week 0 and restaging at Weeks 48 and 96 to confirm maintenance of Stage D0 disease.
- Sample size: N = 72 (6 lead-in patients for safety assessment, 2:1 randomization: TARP N = 44; placebo N = 22).

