**Figure 9**

## 3.2 VACCINE ADMINISTRATION

The vaccine manufacturing schema is described in **Appendix C** and manufacturing procedures will follow the NIH Center for Cellular Engineering (CCE) Protocol Specific Instructions (PSI) and Standard Operation Procedure (SOP). All patients will undergo 15-18L apheresis to remove peripheral blood monocytes for dendritic cell preparation as well as peripheral blood mononuclear cells for flow cytometry and immunologic studies at their Week 0 visit. Cells used for subsequent dendritic cell maturation will be derived from monocytes frozen during the initial apheresis. Apheresis may be repeated any time if additional plasma or cell aliquots are needed to manufacture the vaccine. Eligible subjects will receive autologous ME TARP dendritic cell or elutriated monocyte vaccine placebo beginning at Week 3. Each dose can be delivered starting from -1 week of the target date until the maximum delay described in Section **3.3.2**. Patients will be assessed prior to each dose, no earlier than 10 days prior to the administration of the

investigational product. This assessment will include a CBC, acute care panel and liver panel. Refer to [Appendix C](#) for details concerning the cGMP production of peptide-pulsed dendritic cells and elutriated monocyte placebo by the NIH Clinical Center Department of Transfusion.

- Autologous ME TARP DC and elutriated monocyte placebo vaccine preparations will be assessed for release standards (nucleated cell content and concentration, appearance, flow cytometric verification of DC validation markers, viability  $\geq 60\%$ , and product sterility and safety testing) prior to release for vaccine administration to the patient.
- For both groups, the investigational product will be administered intradermally in two sites on the forearm with a maximum volume of 0.5 mL per injection. Administration will be alternated between the left and right forearms with each vaccination, with the exception of patients with a contraindication to using a particular arm. In these instances, consecutive doses in the same arm will be allowed. All patients will receive a total of 6 doses of vaccine ( $20 \times 10^6$  *viable* cells/dose,  $+\/- 10\%$ ) delivered at Weeks 3, 6, 9, 12, 15, and 24 and will undergo scans at Weeks 48 and 96 for restaging.

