11. An enrollment log will be maintained in the regulatory binder/file that is the only location of personal identifiers with unique subject identification number.

The PI will be responsible for overseeing entry of data into an in-house password protected electronic system (C3D) and ensuring data accuracy, consistency and timeliness. The principal investigator, associate investigators/research nurses and/or a contracted data manager will assist with the data management efforts. All data obtained during the conduct of the protocol will be kept in secure network drives or in approved alternative sites that comply with NIH security standards. Primary and final analyzed data will have identifiers so that research data can be attributed to an individual human subject participant.

All adverse events, including clinically significant abnormal findings on laboratory evaluations, regardless of severity, will be followed until return to baseline or stabilization of event. Serious adverse events that occur more than 6 weeks after the last administration of investigational agent/intervention and have an attribution of at least possibly related to the agent/intervention should be recorded and reported as per sections [Error! Reference source not found.](#) and [7.4](#).

AEs will be documented starting with the first study intervention through 60 days following the last administration of vaccine. Adverse events that are serious need to be recorded after 60 days following the last intervention, only if they are serious and related to the study intervention.

An abnormal laboratory value will be considered an AE if the laboratory abnormality is characterized by any of the following:

- Results in discontinuation from the study
- Is associated with clinical signs or symptoms
- Requires treatment or any other therapeutic intervention
- Is associated with death or another serious adverse event, including hospitalization.
- Is judged by the Investigator to be of significant clinical impact
- If any abnormal laboratory result is considered clinically significant, the investigator will provide details about the action taken with respect to the test drug and about the patient's outcome.

**End of study procedures:** Data will be stored according to HHS, FDA regulations and NIH Intramural Records Retention Schedule as applicable.

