### **12.4 EVALUATION OF BENEFITS AND RISKS/DISCOMFORTS**

The potential benefit of vaccination with multi-epitope TARP peptides is unknown. Although a majority of patients (~72%) in our first 09-C-0139 TARP peptide vaccine study exhibited a decline in the slope log PSA compared to their Pre-NIH slope that was sustained out to 48 weeks, these responses were associated with absolute declines in PSA levels in only a minority of patients (~15% of responders). In addition, it is unknown and unproven whether slowing PSA velocity through vaccination or any other treatment intervention, will in turn impact clinical outcomes. Ongoing long-term observation out to 144 weeks on the 09-C-0139 study suggests that responses to TARP vaccination may wane. In addition, there were study subjects who had objective evidence of clinical progression following an initial, favorable slowing in PSA velocity. We believe that this second generation multi-epitope TARP vaccine comprised of longer synthetic peptides will include MHC class II CD4+ T cell helper epitopes that will allow generation of better CD8+ T cell responses with improved functional avidity and longevity (42) as well as humoral anti-TARP antibody responses.

TARP peptide vaccination was shown to be safe and very well tolerated in the 09-C-0139 study and we think it is highly likely that the multi-epitope TARP vaccine will have a similar, favorable safety and tolerability profile. Vaccination was also associated with induction of TARP-specific cellular immune responses in a majority of patients (~75%) as well. However the clinical significance of these immune responses remains unknown. In this study, we will attempt to definitely establish whether the observed declines in the difference in the slope log (PSA) documented in the 09-C-0139 study are real and not due to spontaneous or random slowing in the rate of PSA rise. We will also conduct an exploratory assessment of progression free survival (PFS) at 96 weeks to see if there is any indication of efficacy regarding clinical outcomes in patients receiving autologous ME TARP DC vaccination. The most significant risk for study subjects randomized to receive the autologous elutriated monocyte vaccine placebo is the apheresis required to collect cells, as autologous, minimally manipulated thawed elutriated monocytes are unlikely to be associated with any adverse reactions other than local injection site discomfort.

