## 15 APPENDICES

### 15.1 APPENDIX A: STUDY CALENDAR OF CLINICAL AND LABORATORY EVENTS

Study Procedures	Screening  /Apheresis	Wk 3  (Baseline  )	Wk 6 	Wk 9 	Wk 12 	Wk 15 	Wk 18 	Wk 24 	Wk 36 	Wk 48 	Wk 60 	Wk 72 	Wk 84 	Wk 96 	Post Therapy Follow up 
NIH Advance Directives Form 	X														
History & Physical	X	X	X	X	X	X	X	X	X	X	X	X	X	X	
ECOG Status	X	X	X	X	X	X	X	X	X	X	X	X	X	X	
Height	X														
Weight	X	X	X	X	X	X	X	X	X	X	X	X	X	X	
Vital Signs	X	X	X	X	X	X	X	X	X	X	X	X	X	X	
CBC w/ diff	X	X	X	X	X	X	X	X	X	X	X	X	X	X	
PT/PTT	X														
Acute/Hepatic /Mineral Panel	X	X	X	X	X	X	X	X	X	X	X	X	X	X	
TTV Screen  , ABO 	X														
PSA / Testosterone	X	X	X	X	X	X	X	X	X	X	X	X	X	X	
PSADT Calculation 	X														
Bone Scan	X													X	

Study Procedures	Screening  /Apheresis	Wk 3  (Baseline  )	Wk 6 	Wk 9 	Wk 12 	Wk 15 	Wk 18 	Wk 24 	Wk 36 	Wk 48 	Wk 60 	Wk 72 	Wk 84 	Wk 96 	Post Therapy Follow up 
CT Scan (C/A/P)	X									X					X
EKG	X														
Informed Consent	X														
Apheresis 	X														
Urinalysis		X								X					X
TSH		X		X			X		X	X	X			X	X
25-OH Vit D level			X		X			X		X	X	X			X
Amylase/Lipase/ Lipid panel			X							X					X
HLA typing		X													
Lymphocyte phenotyping		X			X			X		X	X	X			X
DC vaccine		X	X	X	X		X		X						
Vaccine Report Card		X	X	X	X		X		X						
Adverse Events		X	X	X	X		X		X	X	X	X			X
Concomitant Medications	X	X	X	X	X		X		X	X	X	X			X
Phone/mail follow up															
Research Correlatives															

Study Procedures	Screening  /Apheresis	Wk 3  (Baseline  )	Wk 6 	Wk 9 	Wk 12 	Wk 15 	Wk 18 	Wk 24 	Wk 36 	Wk 48 	Wk 60 	Wk 72 	Wk 84 	Wk 96 	Post Therapy Follow up 
Anti-TARP Ab		X		X 	X		X	X	X	X	X	X	X	X	X
CTCs, immune subsets		X		X		X	X	X	X	X	X	X	X	X	X
PBMCs Cellular Responses		X		X 	X		X	X	C	X	X	X	X	X	X

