1. As indicated in section **12.2**, all subjects  $\geq$  age 18 will be offered the opportunity to complete an NIH Advance Directives form. This should be done preferably at baseline but can be done at any time during the study as long as the capacity to do so is retained. The completion of the form is strongly recommended but is not required.
2. TTV Screening (Anti-HIV-1/2 Ab, anti-HCV Ab, HBsAg, HBs Ab, anti-HTLV-1/2 Ab, West Nile, T. Cruzi and RPR) must be drawn at the time of screening but for the consent, only HIV, HBV and HCV results are required to enroll. If the day of apheresis is  $>30$  days from the initial TTV screening, TTV screening needs to be repeated to be compliant with DTM requirements.
3. Historic records are acceptable if previous NIH results are available.
4. PSADT will be calculated only when the patient is in D0 prostate cancer.
5. Apheresis should occur within 3 weeks after consenting. The first dose of investigational drug should be scheduled within 6 weeks after the consent is signed. Apheresis may be repeated if additional plasma or cell aliquots are required to manufacture the vaccine.
6. Screening studies including scans should occur within 60 days of enrollment at the NIH unless otherwise specified (see section **2.2.2**).
7. Evaluation to proceed with vaccine administration should occur within 10 days prior to administration. Study weeks will be numbered so that they match vaccine dose weeks, in case off-target dates in investigational product administration occur. The dosing interval should be at least 14 days.
8. Evaluations at Week 3 serve as baseline. If amylase, lipase, lipid panel, TSH, 25-OH Vitamin D, lymphocyte phenotyping, urinalysis have already been completed within 30 days prior to the first dose of administration of investigational product, they do not need to be repeated at the baseline (Week 3) timepoint. Historic HLA-ABC, DR results from NIH may be used for baseline.
9. Post-therapy follow up, with the patient or patient's local oncologist, will occur annually until disease progression or death.
10. Research correlatives on week 12 (post 3 doses of investigational treatment) may be collected 7 days (+/- 3 days) post 3rd dose of investigational treatment, if patient is available locally.

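### Mandatory SAE reporting to the sponsor starts at the first dose, so a serious event from the Week 0 apheresis is not clearly required to be reported

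*Combined protocol and SAP*

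**What the plan says.** The procedure comes before the product. The Précis states "All patients will undergo a 15-18L apheresis at Week 0", and section 3.2 states "Eligible subjects will receive autologous ME TARP dendritic cell or elutriated monocyte vaccine placebo beginning at Week 3". Footnote 5 of Appendix A asks for apheresis within 3 weeks of consent and adds: "The first dose of investigational drug should be scheduled within 6 weeks after the consent is signed". Section 12.4 says of the control arm: "The most significant risk for study subjects randomized to receive the autologous elutriated monocyte vaccine placebo is the apheresis required to collect cells".

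The safety sections start the clock at different points:

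- Section 6.1: "AEs will be documented starting with the first study intervention through 60 days following the last administration of vaccine". The protocol does not say whether apheresis counts as an intervention for this purpose.
- Section 8.2 refers to 6.1 for the recording period and then, in the next sentence, sets its own start for sponsor reporting: "All serious adverse events recorded from the time of first investigational product administration must be reported to the sponsor".
- Section 8.3 requires SAEs to be submitted within 24 hours of awareness and gives no start date.
- In Appendix A, the "Adverse Events" row is empty in the Screening/Apheresis column and first marked at Wk 3. The Concomitant Medications row is marked in both columns.

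On causality, section 8.1.5 says: "All AEs will have their relationship to study product assessed using the terms: related or not related". It has no category for relationship to a study procedure.

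**The concern.** The protocol names apheresis as the chief hazard for patients who receive placebo. It then starts mandatory sponsor reporting, and the calendar's prompt to collect adverse events, after that hazard has passed. The procedure is invasive. Appendix C processes large blood volumes, allows a venous catheter (for the placebo preparation, a temporary femoral central line), and provides for calcium and magnesium infusions against citrate toxicity.

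A site that follows 8.2 and the calendar literally could have a serious catheter or citrate event at Week 0 and find no clear instruction to send it to the sponsor. Sites could also differ in practice, because 6.1, 8.2 and 8.3 support different answers. The stake is oversight of harm from a procedure that every patient must undergo.

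**Working it through.** The plan states no figure for this interval, so there is nothing to reproduce. The check is a comparison of start points with some simple date arithmetic.

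**Inputs.** Apheresis at Week 0 (Précis; section 3.2). First dose at Week 3 (section 3.2). Apheresis 0 to 3 weeks after consent and first dose no later than 6 weeks after consent (Appendix A, footnote 5). Planned patients: 6 lead-in, 44 active, 22 placebo; accrual ceiling 75 (section 10).

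**Length of the gap.**

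- Nominal: Week 3 − Week 0 = 3 weeks = 21 days.
- Footnote 5: gap = (consent to dose 1) − (consent to apheresis). With dose 1 at its limit and apheresis on the day of consent, 6 − 0 = 6 weeks = 42 days. With apheresis at its own limit, 6 − 3 = 3 weeks.
- Section 3.2 also lets each dose slip to the maximum in section 3.3.2, which is up to 6 weeks for cell-processing or regulatory reasons. Applied to dose 1, that gives Week 3 + 6 = Week 9. The protocol does not say how this fits with footnote 5, so the size quoted here does not rely on it.

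**Patients exposed.** 6 + 44 + 22 = 72, of whom 22 are on placebo.

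**A serious event at the Week 0 apheresis, set against each rule.**

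| Place | Start point | Effect on this event |
|---|---|---|
| 6.1 | First study intervention, undefined | Documented if apheresis counts as one, otherwise not |
| 8.2 | First product administration | Outside the mandatory sentence |
| 8.3 | None given | Can be read as requiring submission |
| Appendix A, adverse event row | Wk 3 | No prompt to collect |
| 7.2.1 | Set by NIH policies | IRB route, not the sponsor SAE route |
| 7.3 | Research intervention, within 30 days | Deaths only (not from progressive disease), to the Clinical Director |

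If apheresis is a study intervention, the event is documented under 6.1, but 8.2 does not require it to go to the sponsor. If it is not, neither sentence applies. The adverse event definition in 8.1.1 is framed around a subject who has been given a pharmaceutical product, which leans towards the narrower reading. Only 8.3, taken alone, would bring the event in.

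**Never-dosed patients.** Section 3.5.1 foresees persistent failure of a product to meet release criteria. If that happens before dose 1, the event that starts the 8.2 clock never occurs.

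**Limits of the check.** The calendar was damaged in text extraction and some later marks are displaced. The empty leading cell in the adverse event row is clear. A repeat apheresis after dose 1 falls inside the 8.2 window, so the gap concerns the Week 0 procedure and any repeat before dose 1.

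**The case against.** The best reply is that 8.2 sets a minimum and excludes nothing. Section 8.3 is the operative reporting section. It covers any event that meets the serious criteria, has no start date, and sends reports to the Center for Cancer Research, which is the sponsor. A careful site could report a Week 0 SAE under it. This stands as far as it goes, and it is why the point is an unclear requirement and not a proven exclusion. It does not remove the problem: 8.2 contains the only sentence that dates sponsor reporting, and a mandatory duty should not depend on which section the site follows.

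Three stronger readings are tempting, and the documents do not support them:

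- **That such events would never reach FDA.** Under section 8.5, expedited FDA reports depend on evidence of causation by the study product, so an apheresis event before any dose would not qualify whatever start date 8.2 used. The same section sends all serious events to FDA at least annually.
- **That the cause would be lost because the event is rated not related.** Section 8.2 requires an alternate etiology for events judged unrelated to product, so apheresis or the catheter can be named. Not related to product would also be the correct product attribution.
- **That apheresis harm would be missing from the safety objective.** The objective in section 1.1.2 concerns the safety of vaccination, and 6.1 may still have the event documented.

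The Appendix A column also combines screening with apheresis, and section 2.2.2 places screening under a separate protocol. An unqualified mark there would extend adverse event collection too far. That is a fair criticism of a simple tick.

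**Conclusion.** The point holds as a mismatch of start dates with a safety consequence. As written, an SAE from the Week 0 apheresis is not clearly required to reach the sponsor. The interval is nominally 3 weeks and up to about 6 weeks under footnote 5. It applies to all 72 planned patients, and a patient who is never dosed has no start date under 8.2 at all.

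This rests on taking the 8.2 sentence as the governing start for sponsor reporting, and on 6.1 leaving its own start undefined. The 6-week figure is a scheduling extreme that assumes apheresis on the day of consent. The documents give no rate of serious apheresis events, so the expected number affected cannot be estimated.

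A reader might infer that no apheresis harm would be recorded, or that its reporting to FDA is blocked. Neither follows. Section 8.3 and the alternate-etiology entry may capture some of these events, and deaths and NIH policy events have their own routes. The change is still worth making, because following 8.2 and the calendar literally leaves a required invasive procedure outside mandatory sponsor reporting.

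**What to change.** 1. In 6.1, define the first study intervention as including the Week 0 apheresis.
2. In 8.2, use that same start for SAE reporting to the sponsor, and check that the definition in 8.1.1 is not read to exclude events before the first dose.
3. In Appendix A, mark adverse events from apheresis onward, with a footnote that this does not cover screening under the separate protocol.
4. Optionally, in 8.1.5, record relationship to study procedure (apheresis or catheter access) alongside relationship to study product.

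The cost is protocol wording, one calendar mark, a few more SAE reports and, if item 4 is adopted, one CRF field. Patients are already on site for the procedure. No dose, schedule or treatment rule changes.
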